6.4.3 Returns and Destruction

If any IP is discarded or lost in the study site, the manager will record relevant details in the IP accountability log. In principle, disposal of the IPs at the study site is not allowed. When the study ends, any unused IPs that have not been administered to the subjects or returned by the subjects after administration should be returned to the assigned CRO or the location specified by the sponsor. A certificate of return should be attached when sending the IPs to confirm any drugs to be returned.

7 Study Methodology and Dosing Schedule

7.1 Overall Study Methodology

Screening Period

Subjects will provide written informed consent to participate in the study and then undergo any screening. Subjects who meet all the inclusion criteria and none of the exclusion criteria based on the screening test results will be included into the study.

Treatment Period

The subject will receive the IP consumed once daily for 1 week at Visit 2 (Day 0). Subjects will have a site visit 1 week after IP administration and prescribed the IP for another 3 weeks at Visit 3 (Day 7 ± 3 days). Subjects will visit the study at Visit 4 (Day 28 ± 5 days) to determine healing status by Gastroesophageal Reflux Questionnaires (GERD-Q).

Subjects who have not been healed at Visit 4 (Day 28 ± 5 days) will have an additional IP administration period for 4 weeks and then visit the study site at Visit 5 (Day 56 ± 5 days) to determine healing status.

If, a subject withdrawn during the treatment period will visit the study site within 2 weeks from the withdrawal decision and undergo the Withdrawal visit procedures. However, they will not be conducted if the subject refuses them.

Follow up Period

Subjects will have a Safety F/U visit within 2 weeks (± 5 days) from the day when healing is confirmed. (However, this visit will be carried out by a telephone visit. If necessary, additional examination and treatment may be performed according to the investigator's judgment.)

[figure not shown]

Figure 2. Study Schematic

7.2 Dosage, Administration and Duration of Investigational Product

7.2.1 Dosage and Duration of Administration

- ① Study group (Fexuprazan 40 mg)
 - Fexuprazan 40 mg 1 tablet
- ② Control group (Esomeprazole 40 mg)
 - Esomeprazole 40 mg 1 capsule

7.2.2 Administration Method

For maximum 8 weeks from the next day of investigational product dispensing, 1 tablet/capsule will be administered orally once daily without regard to meals. Tablets/Capsules should be taken at a regular time.

7.3 Concomitant and Prohibited Therapies

7.3.1 Permitted Concomitant Therapies

Concomitant therapies (medication or treatment) unless included in the prohibited medications may be implemented if medically indicated at the discretion of the investigator. Ingredient name (or brand name), regimen and dosage (amount of 1 dose, dose unit, frequency of administration, route of administration), duration of administration (start date of administration, during administration, end date of administration), and purpose of concomitant medication taken during the study should be recorded on the case report form. Only Antacid and Prokinetic permitted as rescue drug.

7.3.2 Concomitant and Prohibited Therapies

- Non-steroidal anti-inflammatory drugs (aspirin, etc.) and acetaminophen
 - : a low dose of aspirin (≤ 100 mg/day) which has been administered for the purpose of prevention before participating in the study is allowed
 - : acetaminophen administration is allowed up to 4 g/day and does not exceed 5 days in 4 weeks
- Acid suppressive drugs: Proton pump inhibitors (PPIs), acid pump antagonists, H2 receptor antagonists, anti-gastrin agents
- Cholinergic drugs, anticholinergic drugs, and antispasmodics
- Psychotropic drugs: Antipsychotics drugs, antidepressants, antimanic drugs, antianxiety drugs, and hallucinogenic agents, etc.
- Steroids (allowed if used in a local application)
- Antithrombotic drugs (antiplatelet drugs and anticoagulants)
- Mucoprotective drugs

7.3.3 Treatment Compliance

In order to ensure the validity of research data related to the ability of IP to relieve symptoms and ensure safety in subjects, also to gain a better understanding of drug performance in real-world settings and improve the quality of study outcomes, at each visit after the administration of the IP, all subjects should return the unused IP prescribed at the previous visit and empty packaging, and the sub-investigator (or a designee) will check the number of tablets/capsule to be taken, number of tablets/capsules actually taken, and number of returned and unreturned tablets/capsules and record them on the case report form at each visit.

$$\text{Treatment compliance (\%)} = \frac{\text{Number of tablets/capsules actually taken}}{\text{Number of tablets/capsules to be taken}} \times 100$$

8 Study

Procedures and Assessments

8.1 Visit Schedule

Subjects will provide written informed consent to participate in the study and then undergo any screening. Subjects who meet all of the inclusion criteria and none of the exclusion criteria based on the screening test results will be included into the study. Subjects will have a site visit 1 week after IP administration. Subjects will visit the study site again in person 4 weeks after the first IP administration to determine healing status with symptoms relief at Week 4 measured by GERD-Q Score <8 . Healed subjects will have a Safety F/U visit after 2 weeks (± 5 days) and unhealed subjects will take the IP for additional 4 weeks and then visit the site to determine healing status with symptoms relief at Week 8 measured by GERD-Q Score <8 . The Safety F/U visit will be conducted 2 weeks (± 5 days). The Safety F/U visit will be conducted via telephone visit and subjects will have a visit for additional tests or treatments based on the investigator's judgment.

In the event of withdrawal, the procedures for the Withdrawal visit will also be conducted by visiting the site within 2 weeks after the withdrawal decision is made. See Study Schedule Table for procedures to be performed at each visit.

8.2 Study Schedule Table

	Screening (wash-out)	Treatment 1			Safety F/U ¹¹⁾	Treatment 2 (Unhealed Subject after 4 Weeks of Treatment)	Safety F/U ¹¹⁾	Withdrawal Visit ¹²⁾
Visit	Visit 1 ¹⁾	Visit 2	Visit 3	Visit 4	Visit 4-1	Visit 5	Visit 5-1	
Protocol No.DW_DWP1401262001					30 / 55 page			Protocol Version, 2.1 Version date 2024-06-19

Schedule	Day-14~	Day 0	Day 7	Day 28	Day 42	Day 56	Day 70	
Window	-	-	± 3 day	± 5 day	± 5 day	± 5 day	± 5 day	
Informed consent	O							
Demographic survey	O							
Assessment on symptom questionnaire (GERD-Q) ²⁾	O	O	O	O		O ¹³⁾		O ^{*)}
Quality of Life assessment (GERD-HRQL)		O	O	O		O ¹³⁾		O ^{*)}
Medical and surgical history ³⁾	O	O						
Prior/concomitant medications ⁴⁾	O	O	O	O	O	O	O	O ¹²⁾
Vital signs ⁵⁾	O	O	O	O	O ¹¹⁾	O ¹³⁾	O ¹¹⁾	O ¹²⁾
Physical examination	O	O	O	O	O ¹¹⁾	O ¹³⁾	O ¹¹⁾	O ¹²⁾
Laboratory tests ^{6),7)}	O			O	O ¹¹⁾	O ¹³⁾	O ¹¹⁾	O ¹²⁾
Pregnancy test ^{6),8)}	O	O						
Inclusion/exclusion criteria ⁹⁾		O						
Prescription of IPs ¹⁰⁾		O	O	O ¹³⁾				
Return of IPs and check of treatment compliance ¹⁰⁾			O	O		O ¹³⁾		O ¹²⁾
Distribution of subject diary ¹⁰⁾		O	O	O ¹³⁾				
Collection of subject diary ¹⁰⁾			O	O		O ¹³⁾		O ¹²⁾
Adverse events			O	O	O	O	O	O ¹²⁾

- 1) Visit 1 and Visit 2 can be conducted on the same day.
- 2) Eligibility of subjects will be assessed based on the results from Visit 2 (GERD-Q result from Visit 1 will be used as the eligibility criteria). However, the results may be replaced with the test results obtained within 7 days prior to Visit 2, if available.
- 3) Gastrointestinal medical history and surgical history will be investigated at Visit 1 regardless of the time of previous occurrence and, for other medical history and surgical history, only those which occurred within 6 months from screening or are ongoing at screening and baseline will be investigated.
- 4) For prior medications, information on drugs administered within 4 weeks from the date of the written consent at Visit 1 will be collected. (Only Antacid and Prokinetic permitted as rescue drug)
- 5) Vital signs: After resting in a sitting position for 5 minutes or longer, blood pressure (diastolic/systolic), pulse rate, and body temperature will be measured.
- 6) The relevant tests can be replaced with the test results obtained from the same institution within 2 weeks from Visit 1, if available.
- 7) Laboratory tests will be conducted to check the inclusion/exclusion criteria and assess the safety (Visit 1, Visit 4, Visit 5, Withdrawal visit, and Safety F/U). At Visit 1, a re-test may also be conducted once according to the investigator's judgment and, in such a case, evaluation will be based on the results of re-test.

① Hematology	WBC with differential count (neutrophil, lymphocyte, monocyte, eosinophil, basophil), RBC, hemoglobin, hematocrit, platelets
② Blood Chemistry	Random blood glucose, ureum, uric acid, AST, ALT, creatinine, total bilirubin
③ Blood Coagulation test	PT, INR, APTT
④ Urinalysis	pH, specific gravity, albumin, bilirubin, glucose, urobilinogen, ketone, nitrite, occult blood, microscopy (urine RBC, urine WBC)

- 8) Pregnancy test will be performed with serum or urine pregnancy test will be performed at Visit 1. (Women who medically do not have child-bearing potential are exempt from the pregnancy test). If Visit 1 and Visit 2 are conducted on the same day, another pregnancy test (serum or urine test) should be conducted prior to IP administration even if the test result within 2 weeks before the date is available.
- 9) Eligibility of subjects will be assessed based on the results from Visit 2 (However GERD-Q result from Visit 1 will be used as the eligibility criteria).
- 10) Subjects who have not symptoms relief at Visit 4 will be prescribed the investigational product for treatment 2, and

subject diary will be distributed to them. At Visit 5, treatment compliance will be checked, and subject diary will be collected only from those who have undergone Treatment 2.

(#: Subject diary completion will be checked at Visit 3, and appropriate training on diary keeping will be performed on the phone, if necessary.)

- 11) The Safety F/U will be conducted as a telephone visit within 2 weeks (\pm 5 days) from Visit 4 only in subjects who complete all protocol-specific treatments, and the subjects may visit for additional tests or treatments based on the investigator's judgment.
- 12) If a subject decides to discontinue participation or is withdrawn from the study before completion, the Withdrawal visit procedures will take place within 2 weeks from the withdrawal decision. At the Withdrawal visit, the unused IPs or empty packaging will be returned, and the subject diary will be collected. However, assessment of Gastroesophageal Reflux Disease Questionnaire (GERD-Q)^{*)} and quality of life questionnaire (GERD-HRQL)^{*)} must be performed. If the patient refused to visit, above two Questionnaires can be done by telephone call and the document should be written on the EMR by the investigator.
- 13) Subjects who have not been healed after the Treatment 1 of investigational product administration will have an additional 4-weeks of treatment period (Treatment 2) with the same mode of administration.

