3.4 Criteria for Withdrawal

The subjects are allowed to spontaneously discontinue participation in this study at any time. The investigator may discontinue participation of a subject in this study at any time as per the subject's decision. However, a subject who are terminated early for showing a sufficient level of efficacy of the investigational product will not be considered as a withdrawal. If a subject is withdrawn from the study, the study results obtained from the discontinued/withdrawal case until the time point of discontinuation/withdrawal may be reviewed for evaluable items at the final evaluation.

In following cases, the investigator may withdraw the subject from the study.

- 1) Violation of inclusion/exclusion criteria is identified during the study.
- 2) Subjects are considered difficult to continue with the study due to adverse events as per the investigator's decision.
- 3) Subjects have received or are deemed to require medications or treatments that may affect the study results during treatment period or follow-up period.
- 4) Voluntary consent withdrawal by the subject or subject's legally acceptable representatives.
- 5) Subjects cannot not cooperate with the investigator.
- 6) Lost to follow-up.
- 7) The investigator decides to withdraw subjects.
- 8) Subject is pregnant during the study

If a subject determines to discontinue his/her participation and withdrawn from the study prior to completion, procedures scheduled for the Withdrawal visit should be performed. The procedure for the Withdrawal visit will be conducted within 2 weeks after the withdrawal decision is made. At the Withdrawal visit, the unused IPs or empty packaging will be returned, and the subject diary will be collected.

If the patient refused to visit, the vital sign, physical examination and lab test can be exclude. However, assessment of Gastroesophageal Reflux Disease Questionnaire (GERD-Q) and quality of life questionnaire (GERD-HRQL) must be performed at least by telephone call by the investigator, and all document should be written on the EMR by the investigator.s. To prevent any missing AEs that the investigator is not aware of, all kinds of methods must be employed to directly contact the subjects who refuse to visit such as phone call, letter, or personal visit. Any withdrawn subject cannot participate in the same study again.

4 Description of Study Design

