9.2.3 Efficacy Endpoints

9.2.3.1 Primary Efficacy Assessment

Proportions of subjects with symptoms relief at Week 4

The proportions of subjects with symptoms relief by Week 4 and their 95% confidence intervals will be provided by group.

The proportions of subjects with symptoms relief by Week 4 will be calculated as the cumulative symptoms relief by using the results at the time of final observation including the Withdrawal visit. To compare the control group and study group, the lower bound of the 2-sided 95% confidence intervals will be obtained by using Chi Square test or Fisher's Exact test method. If this lower bound is greater than the non-inferiority margin of -0.1, the study group will be judged to be non-inferior to the control group.

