9.4.2 Rationale for Determination of Sample Size

This study objective is to determine the non-inferiority of the study group (Fexuprazan 40 mg) compared to the control group (Esomeprazole 40 mg) in patients with erosive gastroesophageal reflux disease. The primary endpoint is the proportions of subjects with symptoms relief at week 4 measured by GERD-Q Score <8 , and the hypothesis is:

$$H_0: \pi_T - \pi_C \leq -0.1 \quad \text{vs.} \quad H_A: \pi_T - \pi_C > -0.1$$

π_T : Proportion of subjects with symptoms relief at week 4 (measured by GERD-Q score <8) in the study group (Fexuprazan 40 mg)

π_C : Proportion of subjects with symptoms relief at week 4 (measured by GERD-Q score <8) in the control group (Esomeprazole 40 mg)

The proportion of subjects with symptoms relief at week 4 of proton pump inhibitors (PPI) was considered to be 88.5%, and this value was set as the proportion of symptoms relief for the control group (Esomeprazole 40 mg). In this study, the proportion of symptoms relief of the study drug was assumed to be higher than control drug, therefore, 94.0% was set as the proportion of symptoms relief in the study group.

The number of subjects calculated by “Non-Inferiority Tests for the Difference Between Two Proportions” of PASS2020 with the non-inferiority margin of -0.1, the one-sided significance level of 2.5%, 80% statistical power, and 1:1 randomization allocation, was 53 per group. And considering a dropout rate of 20%, a total of 134 subjects will be enrolled in the study.

Non-Inferiority Tests for the Difference Between Two Proportions											
Numeric Results											
Test Statistic: Z-Test with Pooled Variance											
Hypotheses: H0: P1 - P2 ≤ D0 vs. H1: P1 - P2 > D0											
Target Power	Actual Power*	N1	N2	N	Ref. P2	P1 H0 P1.0	P1 H1 P1.1	NI Diff D0	Diff D1	Alpha	
0.80	0.80729	53	53	106	0.8850	0.7850	0.9400	-0.1000	0.0550	0.025	
* Power was computed using the normal approximation method.											

10 Data Management (Recording, Collection, Access, Protection, and Storage)

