Attachment 2. Gastroesophageal Reflux Disease Questionnaire (GERD-Q)

Screening No.	__S__	Subject No.	__R__			
Subject initial						
Visit No.	 Visit 1	 Visit 2	 Visit 3	 Visit 4	 Visit 5	 Early withdrawal or unscheduled visit

Cobalah mengingat apa yang Anda rasakan dalam 7 hari terakhir						
Berikan tanda centang (v) hanya pada satu tempat untuk setiap pertanyaan dan hitunglah poin GERD-Q Anda dengan menjumlahkan poin pada setiap pertanyaan.						
No.	Pertanyaan	Frekuensi dari skor (poin) untuk gejala				
		0 hari	1 hari	2-3 hari	4-7 hari	
1.	Seberapa sering Anda mengalami perasaan terbakar di bagian belakang tulang dada Anda (heartburn)?	 0	 1	 2	 3	
2.	Seberapa sering Anda mengalami naiknya isi lambung ke arah tenggorokan/mulut Anda (regurgitasi)?	 0	 1	 2	 3	
3.	Seberapa sering Anda mengalami nyeri ulu hati?	 3	 2	 1	 0	
4.	Seberapa sering Anda mengalami mual?	 3	 2	 1	 0	
5.	Seberapa sering Anda mengalami kesulitan tidur malam oleh karena rasa terbakar di dada (heartburn) dan/atau naiknya isi perut?	 0	 1	 2	 3	
6.	Seberapa sering Anda meminum obat tambahan untuk rasa terbakar di dada (heartburn) dan/atau naiknya isi perut (regurgitasi), selain yang diberikan oleh dokter Anda? (seperti obat maag yang dijual bebas)	 0	 1	 2	 3	
Hasil		Bila poin GerdQ Anda \leq 7, kemungkinan Anda tidak menderita GERD Bila poin GerdQ Anda 8-18 , kemungkinan Anda menderita GERD				

*) The Gastroesophageal Reflux Disease Questionnaire has been validated by Marcellus Simadibrata, Aziz Rani, Pangestu Adi, Ali Djumhana, Murdani Abdullah with an article titled “The gastro-esophageal reflux disease questionnaire using Indonesian language: a language validation survey” at May 2011.

Documented date	Date Month Year 20	Documented by	(Signature)

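### In the FAS analysis of the primary endpoint, a withdrawn subject's GERD-Q may be taken up to two weeks after the withdrawal decision and still be scored as relief or failure on the allocated drug

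*Combined protocol and SAP*

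**What the plan says.** **Timing.** Section 3.4 states: "The procedure for the Withdrawal visit will be conducted within 2 weeks after the withdrawal decision is made". Footnote 12 of both schedules (synopsis and Section 8.2) repeats the limit: "the Withdrawal visit procedures will take place within 2 weeks from the withdrawal decision". Both places make GERD-Q and GERD-HRQL compulsory at withdrawal, by telephone if the subject will not attend.

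**Recall.** The GERD-Q form (Attachment 2) opens with "Cobalah mengingat apa yang Anda rasakan dalam 7 hari terakhir", which asks the subject to think back over the last 7 days.

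**Scoring.** Section 9.2.3.1 computes relief by Week 4 "by using the results at the time of final observation including the Withdrawal visit". Section 9.2.3.2 uses the same rule for Week 8.

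**Reasons for withdrawal.** Section 3.4 includes: "Subjects have received or are deemed to require medications or treatments that may affect the study results during treatment period or follow-up period".

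**Analysis sets.** Section 9.2.1 names the PPS and FAS for efficacy and makes the PPS primary. Section 9.1 limits the PPS to FAS subjects who complete without a major deviation, and Section 13.5 lists prohibited medication as a major deviation. The FAS needs one dose and one efficacy result, so it keeps withdrawn subjects, in their randomized group.

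**Refusal.** Section 7.1 says of the withdrawal procedures: "However, they will not be conducted if the subject refuses them".

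**The concern.** No section requires the Withdrawal GERD-Q to fall on study drug, to precede other treatment, or to fall inside a Week 4 window, and none counts withdrawal as non-relief. The LOCF rule in Section 9.2.1 covers continuous endpoints only.

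A subject who stops for lack of effect and starts another acid suppressant can therefore be assessed two weeks later, score below 8, and be counted as a success of the drug that failed. Conversely, a subject relieved on drug who stops for an adverse event can relapse before the visit and be counted as a failure.

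The PPS leaves out withdrawn subjects, so the FAS is the only planned analysis that shows whether leaving them out matters. Its value as that check depends on how these subjects are scored. The trial is also open label, so staff who know the arm can influence when within the two weeks the questionnaire is taken.

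**Working it through.** **1. The plan's own figure.** Section 9.4.2 gives the non-inferiority margin as -0.10 and the control rate as one that "was considered to be 88.5%, and this value was set as the proportion of symptoms relief for the control group". The study-group rate is 94.0%. The result for "the one-sided significance level of 2.5%, 80% statistical power, and 1:1 randomization allocation, was 53 per group". With a pooled-variance Z-test and mean rate (0.885 + 0.940)/2 = 0.9125:

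- Pooled SE = √(2 × 0.9125 × 0.0875 / 53) = 0.0549
- Unpooled SE = √((0.885 × 0.115 + 0.940 × 0.060) / 53) = 0.0546
- Power = Φ((0.055 + 0.10 - 1.96 × 0.0549) / 0.0546) = 0.807

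This matches the stated 0.80729. 53/0.8 rounds up to 67 per arm, 134 in total, as stated. The calculation describes the PPS and is not disturbed by this point.

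**2. Timing.** If the last dose is taken on the day of the decision, a GERD-Q taken 8 to 14 days later has a recall period wholly off drug. A decision on Day 28 allows assessment up to Day 42, whereas Visit 4 closes on Day 33 (Day 28 + 5).

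**3. Does the GERD-Q detect other treatment?** Only in part. A subject with no symptoms scores 3 + 3 = 6 from items 3 and 4. Item 6 adds 1 for extra medicine on one day (total 7, relief) and 2 for two to three days (total 8, not relief). It excludes medicine given by the subject's doctor, so a prescribed acid suppressant adds nothing.

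**4. Weight of one subject.** 67 × 0.20 = 13.4 expected dropouts per arm. One subject is 1/67 = 1.5 points of an arm's FAS rate, or slightly more if the FAS is smaller than 67.

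**5. Direction.** Assume completers have 88.5% relief in both arms, withdrawal fractions are d_T (study) and d_C (control), and a share r of withdrawals is scored as relief in each arm. Then

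difference (T - C) = (d_C - d_T) × (0.885 - r).

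If d_T = d_C, the difference is zero whatever r is. If d_T > d_C, raising r moves it towards fexuprazan; if d_T < d_C, towards esomeprazole.

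**6. Illustration under an assumed imbalance.** Take d_C = 10% and d_T = 10% + 0.10/0.885 = 21.3%, chosen so that the difference is exactly -10 points when every withdrawal is non-relief. With 67 per arm and the Wald 95% lower bound:

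| Share r scored as relief | Control | Study | Difference | P(declare NI), normal approx. | Exact enumeration |
|---|---|---|---|---|---|
| 0 | 0.797 | 0.697 | -0.100 | 2.5% | 2.6% |
| 0.25 | 0.822 | 0.750 | -0.072 | 5.9% | 6.5% |
| 0.50 | 0.847 | 0.803 | -0.044 | 13.6% | 14.8% |
| 0.75 | 0.872 | 0.856 | -0.015 | 29.8% | 31.7% |
| 1 | 0.897 | 0.910 | +0.013 | 59.9% | 62.6% |

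Swapping the arms reverses the sign of each difference.

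**7. Cost of scoring every withdrawal as non-relief.** At the planned rates with 20% withdrawal in each arm, the rates are 0.8 × 0.885 = 0.708 and 0.8 × 0.940 = 0.752, a difference of 0.044.

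- SE = √((0.708 × 0.292 + 0.752 × 0.248) / 67) = 0.0766
- Power = Φ(0.144/0.0766 - 1.96) = 46.8%

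If 25, 50, 75 or 100% of withdrawals score as relief, power is 52.2, 60.4, 72.9 or 90.6%, while the difference stays at 0.044.

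**The case against.** The strongest objection is about scope. A reader might infer that the main result is contaminated because the rule sits under the primary endpoint. The documents do not support that: the PPS is primary and holds completers only, so no Withdrawal GERD-Q enters it. This stands, and confines the point to the FAS. Dropping withdrawn subjects from the PPS is a separate question.

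A reader might also infer a bias towards non-inferiority, since rescue of failures in both arms looks as if it must pull the rates together. This is not established. Step 5 shows no movement when withdrawal and its scoring are balanced, and relapse off drug works the other way. Splits can be built that look alarming. For example, 5 study against 2 control withdrawals wrongly scored as relief gives 3/67 = 4.5 points, and a net 7 gives 10.4 points. The documents give no basis for such a split, and a net 7 would be more than half of one arm's expected dropouts.

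Three further limits stand. Two weeks is a maximum, and the plan does not say that study drug stops at the decision, so off-drug scoring is possible rather than certain. Some dropouts will be lost to follow-up and have no Withdrawal score. Whether withdrawal should count as non-relief or be scored as observed is a choice of estimand, and step 7 shows that the strict choice is costly in power.

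On refusal, Section 7.1 may concern refusal of the procedures, and Section 3.4 and footnote 12 refusal to attend. Even so, one text drops the GERD-Q and the others make it compulsory.

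**Conclusion.** The point holds for the FAS analysis of the primary endpoint, and for the Week 8 endpoint, which uses the same rule. A site and an analyst who follow the plan exactly can count a score from off-drug or otherwise-treated days as the outcome of the allocated drug, in either direction.

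Up to about 13 of 67 subjects per arm are exposed, at about 1.5 points each against a 10-point margin. That range assumes the planned 20% dropout and a Withdrawal score from each of them. The table in step 6 shows how sensitive the FAS conclusion could be under one assumed imbalance. It is not a forecast and does not establish a bias in favour of fexuprazan. The primary PPS analysis and the sample size are unaffected. The change should be made because the FAS is the planned check on the PPS.

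**What to change.** 1. In Section 3.4, Section 7.1 and footnote 12 of both schedules, collect GERD-Q and GERD-HRQL when withdrawal is decided, by telephone if needed, with the subject giving the answers. Keep the two-week window for the other withdrawal procedures.
2. In Section 9.2.3.1, and for Week 8 in Section 9.2.3.2, state that in the FAS a Withdrawal GERD-Q taken after a prohibited acid suppressant has started does not count as relief. The plan already collects what is needed: concomitant-medication start dates (Section 7.3.1) and daily study-drug intake in the diary (Attachment 4).
3. Add two FAS sensitivity analyses: one with every withdrawal before the Week 4 assessment as non-relief, and one with the Withdrawal score used as observed.
4. Reconcile Section 7.1 with Section 3.4 and footnote 12 on what happens to the questionnaires when a subject refuses.

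The cost is protocol wording, one derivation rule, a little more analysis and a somewhat lower FAS relief rate. The analysis that scores all withdrawals as non-relief has only about 47% power at 20% withdrawal per arm under the planned rates, so it should remain a sensitivity analysis.
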